3.2 Inclusion Criteria

Subjects must meet all the following criteria:

- 1) Male and female adults aged 18 to 60 years at the date of the written informed consent form.
- 2) Those who had experienced heartburn and/or acid regurgitation confirmed with:
 - a. GERD-Q Score >7 and
 - b. People who have experienced heartburn symptoms > 3 days within the last 7 days, or
 - c. People who have experienced acid reflux (symptom of acid reflux or back flowing of contents from stomach into the esophagus) > 3 days within the last 7 days
- 3) Those who could understand the provided information and able to fill out the questionnaire and subject diary.

4) Those who voluntarily decided to participate in the study and wrote the informed consent form.

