8.3.3 Questionnaire assessment

- Gastroesophageal Reflux Disease Questionnaires (GERD-Q) (See Appendix 3)
 - The subject will complete the GERD-Q at the screening visit (Visit 1) and Visit 2. The test results from Visit 1 will be used as the basis to determine eligibility for inclusion/exclusion.
 - The subjects who meet the inclusion criteria will complete the GERD-Q at Visit 3, Visit 4, and Visit 5.
- Quality of Life assessment (GERD-Health Related Quality of Life, GERD-HRQL) (See Appendix 4)
 - The subjects who meet the inclusion criteria will complete the GERD-HRQL questionnaire at Visit 2, Visit 3, Visit 4 and Visit 5.^[19, 20, 21]

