8.4 Efficacy Assessment

8.4.1 Efficacy Endpoints

8.4.1.1 Primary Efficacy Endpoint

Proportions of subjects with symptoms relief at week 4 measured by GERD-Q Score <8

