9.2 Statistical Analysis Method

9.2.1 General Principles of Result Analysis

The efficacy analysis will be conducted primarily on the PPS and FAS, and the PPS will be the primary analysis set.

In principle, all statistical analyses will use SAS® version 9.4 or higher and be performed with a two-sided test at a significance level of 5%, unless otherwise specified.

Descriptive statistics (mean, standard deviation, median, minimum, and maximum) will be calculated and provided for continuous variables, and the frequency and percentage will be provided for categorical variables.

The last observation carried forward (LOCF) method will be applied for correction of missing data of continuous endpoints among efficacy endpoints, and if the LOCF method cannot be applied, the raw data will be analyzed without correcting the missing data. However, the quality-of-life score (GERD-HRQL) will be analyzed using the raw data without applying the LOCF. For survival analysis, censoring will be utilized. When applying the LOCF, if the value immediately before the missing value is the baseline value, it will not be replaced.

The missing values of efficacy endpoints will be handled for both analyses on the FAS and PPS, and the safety endpoints will be analyzed with the raw data without replacing the missing values.

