9.2.3 Efficacy Endpoints

9.2.3.1 Primary Efficacy Assessment

Proportions of subjects with symptoms relief at Week 4

The proportions of subjects with symptoms relief by Week 4 and their 95% confidence intervals will be provided by group.

The proportions of subjects with symptoms relief by Week 4 will be calculated as the cumulative symptoms relief by using the results at the time of final observation including the Withdrawal visit. To compare the control group and study group, the lower bound of the 2-sided 95% confidence intervals will be obtained by using Chi Square test or Fisher's Exact test method. If this lower bound is greater than the non-inferiority margin of -0.1, the study group will be judged to be non-inferior to the control group.

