- Descriptive statistics (mean, standard deviation, median, minimum, and maximum) of the proportions of days free of any heartburn, acid regurgitation, or heartburn/acid regurgitation for the first 7 days, full 4 weeks, and full 8 weeks from the first IP administration will be presented for daytime, nighttime, and daytime/nighttime by group. For comparison between treatment groups, an ANCOVA model will be applied with treatment group as a treatment effect. The results of ANCOVA model will be summarized as the LSM differences between the study group and the control group, the corresponding 2-sided 95% confidence interval, and p-value.
(Week 8 evaluation will only be applicable to patient receiving treatment 2)

3. Assessment on symptoms of reflux disease using GERD-Q

Descriptive statistics (mean, standard deviation, median, minimum, and maximum) for the changes from baseline in frequency at the first 7 days, 4 weeks, and 8 weeks will be presented by time point. For the changes from baseline in variables measured at the first 7 days, 4 weeks, and 8 weeks after the IP administration, an ANCOVA model including treatment group as treatment effect, and baseline value will be applied. The results of ANCOVA model will be summarized as the least squares mean (LSM) and standard error by treatment group, the LSM differences between the study group and the control group, the corresponding 2-sided 95% confidence interval, and p-value
(Week 8 evaluation will only be applicable to patient receiving treatment 2)

4. Quality of life assessment using GERD-HRQL

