9.3 Criteria

Hypothesis: The study group (Fexuprazan 40 mg) is non-inferior to the control group (Esomeprazole 40 mg) in terms of the proportions of subjects with symptoms relief by Week 4.

To determine the noninferiority of the study group (Fexuprazan 40 mg) against the control group (Esomeprazole 40 mg), the **Chi Square test or Fisher's Exact test method** will be used. The lower limit of the 2-sided 95% confidence intervals for the difference between the study group and control group (study group minus control group) will be calculated, and if this lower limit is larger than the non-inferiority margin of -0.1, the study group will be declared non-inferior to the control group.

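### The primary non-inferiority comparison is valid but unadjusted; if baseline GERD-Q predicts relief, adjusting for it would recover some precision on the deciding test at little cost

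*Combined protocol and SAP*

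**What the plan says.** The primary endpoint (8.4.1.1) is "Proportions of subjects with symptoms relief at week 4 measured by GERD-Q Score <8". For its analysis, 9.2.3.1 states that "the lower bound of the 2-sided 95% confidence intervals will be obtained by using Chi Square test" or Fisher's exact test, and non-inferiority is declared if the bound exceeds -0.1. Section 9.3 repeats the rule for "The lower limit of the 2-sided 95% confidence intervals for the difference between the study group and control group", and the synopsis agrees. None of the three names a covariate, and no adjusted sensitivity analysis is planned. On the analysis set, 9.2.1 says that "the PPS will be the primary analysis set".

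The entry criterion in 3.2 uses the same instrument: "GERD-Q Score >7 and" frequent heartburn or acid reflux. Section 8.3.3 says "The subject will complete the GERD-Q at the screening visit (Visit 1) and Visit 2", and that the Visit 1 result decides eligibility. Baseline is used elsewhere: for change in GERD-Q symptom frequency, 9.2.3.2 item 3 says that "an ANCOVA model including treatment group as treatment effect, and baseline value will be applied". Item 4 does likewise for GERD-HRQL and adds a symptom factor. The randomisation sections (4.4 and 8.3.12) describe 1:1 allocation and mention no stratification by GERD-Q score.

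**The concern.** Entry and success are cut-offs on one scale. A patient entering at 8 needs a fall of 1 point to reach 7, while one entering at 15 needs a fall of 8. This makes it plausible that the baseline score predicts relief, and a prognostic baseline value is what covariate adjustment uses to reduce residual variance. The covariate will already be in the database.

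The trial is planned at about 80% power, with few failures and one bound that settles the conclusion. If baseline is prognostic, leaving it out makes a true non-inferiority somewhat easier to miss.

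**Working it through.** **Inputs from 9.4.2.** Control rate 0.885, study rate 0.940, margin 0.10, one-sided alpha 0.025, 53 per group, 20% dropout, pooled z-test.

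**1. The plan's own figure.**
- Pooled rate = (0.885 + 0.940)/2 = 0.9125. Pooled SE = sqrt(2 × 0.9125 × 0.0875/53) = 0.0549.
- Unpooled SE = sqrt((0.885 × 0.115 + 0.940 × 0.060)/53) = 0.0546.
- Power = Φ((0.055 + 0.10 - 1.96 × 0.0549)/0.0546) = 0.8073, against the stated 0.80729. At 52 per group it is 0.7998, so 53 is the smallest n.
- 53/0.8 rounds up to 67 per arm, and 2 × 67 = 134.

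The sample size therefore reproduces exactly with no baseline information, consistent with the planned analysis. Expected failures are 53 × (0.115 + 0.060) = 9.3, about 9 in all.

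**2. Analytic range.** Let R² be the share of outcome variance that baseline GERD-Q explains. The documents do not give it, so it is an assumption. Adjustment multiplies the variance of the risk difference by (1 - R²).

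| R² | Power at 53 per arm | 95% half-width | n per arm for 80% | Power if both arms are 88.5% |
|---|---|---|---|---|
| 0 | 80.7% | 0.107 | 53 | 36.5% |
| 0.02 | 81.5% | 0.106 | 51 | 37.1% |
| 0.05 | 82.7% | 0.104 | 50 | 38.0% |
| 0.10 | 84.7% | 0.102 | 47 | 39.8% |
| 0.20 | 88.6% | 0.096 | 42 | 43.8% |

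**3. Simulation.** With about 9 failures, the formula ignores the cost of estimating the covariate effect. Simulation at 53 per arm includes it. The baseline distribution is also assumed: scores 8 to 18, mean about 11, SD about 2. The odds ratio (OR) is for failure per baseline point. The corrected and HC3 columns come from separate runs, each with its own unadjusted comparator. Simulation error is about 0.6 points per power figure at 4,000 trials, sqrt(0.82 × 0.18/4000).

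| OR per point | Unadjusted → standardised difference, small-sample-corrected SE | Change | Unadjusted → linear model, HC3 | Change |
|---|---|---|---|---|
| 1.0 | 82.4 → 82.0 | -0.4 | 82.1 → 80.2 | -1.9 |
| 1.2 | 82.6 → 81.7 | -0.9 | 82.3 → 81.0 | -1.3 |
| 1.4 | 82.9 → 84.0 | +1.1 | 82.5 → 82.1 | -0.4 |
| 1.65 | 82.6 → 85.8 | +3.2 | 83.6 → 84.5 | +0.9 |
| 2.0 | 81.8 → 88.8 | +7.0 | 83.1 → 85.9 | +2.8 |

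One-sided error at true rates of 78.5% and 88.5% was 2.8 to 3.2% adjusted (corrected SE) and 2.6 to 3.2% unadjusted, so the gain is not bought with false positives.

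**4. Standard error.** Without correction, the influence-function SE at OR 2.0 averages 0.0479 against a true SD of 0.0510, a ratio of 0.94. It is about 6% too small, so part of any gain seen with the uncorrected version is under-estimated variance.

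**5. Risk of an empty cell.** The chance of no failures in the study arm at 94% is 0.94^53 = 0.038, about 4%. The logistic model then breaks down and a fallback is needed.

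**The case against.** The strongest case against is that the premise is undocumented and the instrument weakens it. Items 3 and 4 of the GERD-Q (Attachment 2: epigastric pain and nausea) are reverse scored, so a fully symptom-free patient scores 3 + 3 = 6 whatever the baseline. With total = reflux items + reversed items, and the reversed pair worth 0 to 6, a patient entering at 8 with one major symptom at 3 can have a reflux-item sum of 3 to 8. One entering at 12 can have 6 to 12. The ranges overlap, so the total is not a clean severity scale. An OR of 2.0 per point also implies 2^10, roughly a 1,000-fold difference in odds, between scores 8 and 18. All of this stands: it moves the likely gain towards the lower rows of the table and rules out calling baseline a known strong predictor.

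It is also fair that the plan is not inconsistent. Its adjusted models are for continuous change, its other binary endpoints are unadjusted too, and the sample size assumes no covariate.

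A reader might infer more than the documents support:
- **That the unadjusted bound is biased or invalid.** It is neither. Under randomisation the unadjusted interval already allows for chance imbalance in baseline severity.
- **That the expected bound sits close to the margin.** At the planned rates it is about 0.055 - 0.107 = -0.052.
- **That adjustment is free.** It costs up to about 1 point of power if baseline is unrelated or weak, and about 2 with HC3.

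What survives is the balance: a small possible loss against a moderate possible gain, using data already collected.

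**Conclusion.** The point holds as lost efficiency, not as an error. The deciding comparison leaves out a pre-dose measurement of the scale on which success is defined, while the secondary GERD-Q and GERD-HRQL models use baseline. The size depends on an unknown. Power changes by about -1 to 0 points for OR 1.0 to 1.2 per point, +1 at 1.4, +3 at 1.65, and up to +7 only at 2.0. These figures assume 53 evaluable per arm, the planned rates, a baseline distribution not given in the documents, and a small-sample-corrected standard error.

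Adjustment would not rescue the trial if the arms are truly equal: by the formula, power at 88.5% in both arms goes from 36.5% to 43.8% even at R² = 0.20. The assumed 5.5-point advantage (94.0% - 88.5%) matters far more. This is a cheap improvement.

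**What to change.** In 9.2.3.1, 9.3 and the synopsis, before any outcome data are reviewed (the trial is open-label):

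- Make the primary estimate the marginal risk difference, study minus control, standardised over the analysis set from a logistic model with arm and one continuous covariate, the Visit 2 GERD-Q total. Name Visit 2 as baseline, since eligibility uses Visit 1. Add no further terms, because about 9 failures cannot support them.
- Use a small-sample-corrected robust standard error and compare the lower 95% limit with -0.1. The margin is a risk difference, so a conditional odds ratio would not serve.
- Pre-specify a linear model with HC3 errors if an arm has no failures. Alternatively, use that linear model throughout, which avoids switching estimator on the outcome data at the price of a smaller gain.
- Report the unadjusted difference and its interval beside the adjusted result.

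**Cost:** SAP wording and one model, with no new patients, visits or data. The interval is slightly harder to explain, and up to about 1 point of power is given up (about 2 with HC3) if baseline proves not to be prognostic.

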9.2.3.2 Secondary Efficacy Assessment

1. Proportions of subjects with symptoms relief at week 8 measured by GERD-Q Score <8

The proportions of subjects with symptoms relief by Week 8 and their 95% confidence intervals will be provided by group. The proportions of subjects with symptoms relief by Week 8 will be calculated as the cumulative symptoms relief by using the results at the time of final observation including the Withdrawal visit. To compare the control group and study group, the lower bound of the 2-sided 95% confidence intervals will be obtained by using the Chi Square test or Fisher's Exact test method. If this lower bound is greater than the non-inferiority margin of -0.1, the study group will be judged to be non-inferior to the control group. (Week 8 evaluation will only be applicable to patient receiving treatment 2)

2. Assessment on symptoms based on the diary of subjects

- CR (disappearance of heartburn, acid regurgitation, or heartburn/acid regurgitation for 7 consecutive days) is defined as the symptom score of 0 for 7 consecutive days for the first time after the first dose, and the survival time is defined as the time to reach Complete Response (CR) after the first IP administration. Kaplan-Meier plots will be drawn by treatment group, and the medians and their 2-sided 95% confidence intervals will be presented. To compare the control group and study group, the log-rank test will be used.
- The number of subjects without any heartburn, acid regurgitation, or heartburn/acid regurgitation for the first 7 days, full 4 weeks, and full 8 weeks from the first IP administration, the proportion (%) of these subjects and its 95% confidence interval will be presented by treatment group. To compare the control group and study group, the 2-sided 95% confidence intervals and p-value will be obtained by using the Chi Square test or Fisher's Exact test method.
- Descriptive statistics (mean, standard deviation, median, minimum, and maximum) of the proportions of days free of any heartburn, acid regurgitation, or heartburn/acid regurgitation for the first 7 days, full 4 weeks, and full 8 weeks from the first IP administration will be presented for daytime, nighttime, and daytime/nighttime by group. For comparison between treatment groups, an ANCOVA model will be applied with treatment group as a treatment effect. The results of ANCOVA model will be summarized as the LSM differences between the study group and the control group, the corresponding 2-sided 95% confidence interval, and p-value.
(Week 8 evaluation will only be applicable to patient receiving treatment 2)

3. Assessment on symptoms of reflux disease using GERD-Q

Descriptive statistics (mean, standard deviation, median, minimum, and maximum) for the changes from baseline in frequency at the first 7 days, 4 weeks, and 8 weeks will be presented by time point. For the changes from baseline in variables measured at the first 7 days, 4 weeks, and 8 weeks after the IP administration, an ANCOVA model including treatment group as treatment effect, and baseline value will be applied. The results of ANCOVA model will be summarized as the least squares mean (LSM) and standard error by treatment group, the LSM differences between the study group and the control group, the corresponding 2-sided 95% confidence interval, and p-value
(Week 8 evaluation will only be applicable to patient receiving treatment 2)

4. Quality of life assessment using GERD-HRQL

Descriptive statistics (mean, standard deviation, median, minimum, and maximum) for the changes from baseline in the total score of quality of life at the first 7 days, 4 weeks, and 8 weeks will be presented by time point. For the changes from baseline in variables measured at the first 7 days, 4 weeks, and 8 weeks after the IP administration, an ANCOVA model including treatment group as treatment effect, baseline values, and stratification factor (based on dominant symptoms in inclusion criteria: experiencing heartburn, regurgitation, or both of them more than >3 days in the last 7 days) as covariate will be applied. The results of ANCOVA model will be summarized as the least squares mean (LSM) and standard error by treatment group, the LSM differences between the study group and the control group, the corresponding 2-sided 95% confidence interval, and p-value. (Week 8 evaluation will only be applicable to patient receiving treatment 2)

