9.4.2 Rationale for Determination of Sample Size

This study objective is to determine the non-inferiority of the study group (Fexuprazan 40 mg) compared to the control group (Esomeprazole 40 mg) in patients with erosive gastroesophageal reflux disease. The primary endpoint is the proportions of subjects with symptoms relief at week 4 measured by GERD-Q Score <8 , and the hypothesis is:

$$H_0: \pi_T - \pi_C \leq -0.1 \quad \text{vs.} \quad H_A: \pi_T - \pi_C > -0.1$$

π_T : Proportion of subjects with symptoms relief at week 4 (measured by GERD-Q score <8) in the study group (Fexuprazan 40 mg)

π_C : Proportion of subjects with symptoms relief at week 4 (measured by GERD-Q score <8) in the control group (Esomeprazole 40 mg)

The proportion of subjects with symptoms relief at week 4 of proton pump inhibitors (PPI) was considered to be 88.5%, and this value was set as the proportion of symptoms relief for the control group (Esomeprazole 40 mg). In this study, the proportion of symptoms relief of the study drug was assumed to be higher than control drug, therefore, 94.0% was set as the proportion of symptoms relief in the study group.

The number of subjects calculated by “Non-Inferiority Tests for the Difference Between Two Proportions” of PASS2020 with the non-inferiority margin of -0.1, the one-sided significance level of 2.5%, 80% statistical power, and 1:1 randomization allocation, was 53 per group. And considering a dropout rate of 20%, a total of 134 subjects will be enrolled in the study.

Non-Inferiority Tests for the Difference Between Two Proportions											
Numeric Results											
Test Statistic: Z-Test with Pooled Variance											
Hypotheses: H0: P1 - P2 ≤ D0 vs. H1: P1 - P2 > D0											
Target Power	Actual Power*	N1	N2	N	Ref. P2	P1 H0 P1.0	P1 H1 P1.1	NI Diff D0	Diff D1	Alpha	
0.80	0.80729	53	53	106	0.8850	0.7850	0.9400	-0.1000	0.0550	0.025	
* Power was computed using the normal approximation method.											

10 Data Management (Recording, Collection, Access, Protection, and Storage)

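### The Week 8 non-inferiority rule has two conflicting denominators; read literally, it tests about 3 versus 6 subjects selected for failing at Week 4

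*Combined protocol and SAP*

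**What the plan says.** The first secondary endpoint is relief (GERD-Q below 8) at Week 8. Section 9.2.3.2 item 1 gives it a formal decision rule: "If this lower bound is greater than the non-inferiority margin of -0.1", non-inferiority is concluded. Two statements in that paragraph bear on who is counted.

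- Cumulative: "The proportions of subjects with symptoms relief by Week 8 will be calculated as the cumulative symptoms relief", taken at the last observation and including the Withdrawal visit.
- Restricted: the rule ends "judged to be non-inferior to the control group. (Week 8 evaluation will only be applicable to patient receiving treatment 2").

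The synopsis (Statistical Analysis Method) repeats both. The restriction also appears in the endpoint lists (synopsis, Efficacy Endpoints; section 8.4.1.2). Section 8.4.1.2 adds, under the diary item, that the secondary endpoints are assessed only in patients not healed with Treatment 1. The interval is to come from a chi-square or Fisher's exact method; no interval for a difference in proportions is named. Section 9.4.2 sizes the trial for Week 4 only.

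**The concern.** Entry to Treatment 2 depends on the Week 4 outcome, which is observed after randomisation and which the plan itself expects to differ by arm. A comparison confined to those subjects sets one arm's failures against the other's, so randomisation no longer makes the groups alike. The group is also very small for a 10-point margin. This is the only endpoint besides the primary with a declared non-inferiority verdict. A published claim of non-inferiority at Week 8, or an apparent failure to show it, could therefore rest on about nine subjects and on an interval method chosen later. If the cumulative wording governs instead, the comparison stays randomised and these problems largely disappear. The plan does not say which wording governs.

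**Working it through.** **Inputs from section 9.4.2.** Control: "The proportion of subjects with symptoms relief at week 4 of proton pump inhibitors (PPI) was considered to be 88.5" per cent. Study drug: "94.0% was set as the proportion of symptoms relief in the study group". Size: "the one-sided significance level of 2.5%, 80% statistical power, and 1:1 randomization allocation, was 53 per group". Enrolment: "considering a dropout rate of 20%, a total of 134 subjects will be enrolled in the study", that is 67 per arm. Method: "Test Statistic: Z-Test with Pooled Variance". The document gives no Week 8 relief rate, so every Week 8 rate below is an assumption.

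**1. The plan's own figure.** Mean rate (0.885 + 0.940)/2 = 0.9125. With n = 53 per arm:
- SE under the null = sqrt(2 × 0.9125 × 0.0875/53) = 0.0549
- SE under the alternative = sqrt((0.885 × 0.115 + 0.940 × 0.060)/53) = 0.0546
- Power = Φ((0.055 + 0.100 - 1.96 × 0.0549)/0.0546) = 0.807

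This matches the stated 0.80729. 53/0.8 rounds up to 67, giving 134 in total.

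**2. Size of the Treatment 2 group** = n × (1 - Week 4 relief rate).
- 53 per arm: 53 × 0.060 = 3.2 versus 53 × 0.115 = 6.1
- 67 per arm: 67 × 0.060 = 4.0 versus 67 × 0.115 = 7.7

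At 53 per arm the central 95% binomial ranges are 0 to 7 and 2 to 11. The chance of no study-arm subject at all is 0.94^53 = 3.8%.

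**3. Precision at 3 versus 6.** Half-width = 1.96 × sqrt(q(1 - q)(1/3 + 1/6)) for a common Week 8 rate q. This is 0.69 at q = 50% and 0.55 at q = 80%, against a margin of 0.10. For 80% power with equal true rates, n = (1.96 + 0.842)² × 2q(1 - q)/0.1². That is 252 unhealed subjects per arm at q = 80% and 393 at q = 50%.

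**4. Dependence on the interval.** If all nine are relieved (3/3 versus 6/6), the lower 95% limit is 0 by Wald (non-inferior), -0.56 by Newcombe and -0.59 by Miettinen-Nurminen (neither non-inferior). With 3 versus 6 fixed and equal true rates of 30% to 90%, non-inferiority is declared in 0.1% to 5% of trials (Newcombe) or 9% to 47% (Wald). At a true difference of -0.1, Wald still declares it in 7% to 33%.

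**5. Both readings, 53 per arm, with Treatment 2 numbers varying at random.** A trial with an empty Treatment 2 group in either arm counts as no declaration. The columns give the chance of declaring non-inferiority.

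| Assumed Week 8 relief among Week 4 failures, both arms | Subset, Miettinen-Nurminen | Subset, Wald | All subjects, Miettinen-Nurminen |
|---|---|---|---|
| 60% | 3% | 21% | 79% |
| 90% | 0.4% | 50% | 84% |

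Cumulative relief in all subjects is the Week 4 rate plus the failure rate times q. At q = 60% this is 0.940 + 0.060 × 0.6 = 97.6% versus 0.885 + 0.115 × 0.6 = 95.4%.

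**6. One illustration of selection.** Suppose 88.5% would be relieved by either drug at Week 4, 5.5% only by the study drug and 6% by neither. Suppose also that Week 8 relief on either drug is 80% in the 5.5% group and 40% in the 6% group. The study-arm failures then have 40% relief, and the control failures have (5.5 × 0.80 + 6 × 0.40)/11.5 = 59.1%, a difference of -19 points. Cumulative relief is 94 + 6 × 0.40 = 96.4% versus 88.5 + 11.5 × 0.591 = 95.3%, which favours the study drug. Non-inferiority is declared in about 1% (Miettinen-Nurminen) or 10% (Wald) of subset analyses, and in 65% of all-subject analyses (Miettinen-Nurminen).

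**The case against.** The strongest reply is that the parenthesis only says who attends Visit 5, in line with the schedule of activities. A Week 4 responder's final observation is then Visit 4, the subject counts as relieved by Week 8, and the comparison stays randomised. This reading is tenable. A reader might infer that the plan has settled on a Treatment 2-only test and that the Week 8 verdict is therefore meaningless. The cumulative definition in the same paragraph does not support that as a certainty. Nor does the text support the benign reading as settled. The cumulative sentence is carried over from the Week 4 rule, the parenthesis directly follows the decision rule, and section 8.4.1.2 speaks of who is assessed. No passage says that Week 4 responders are carried forward as relieved.

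A reader might also infer that the better drug at Week 4 is bound to be penalised at Week 8 because it leaves a harder-to-treat remainder. The documents do not show this. The -19 points follow from assumed rates and from assuming that nobody is relieved only by the control drug. With equal rates among failures, as in step 5, there is no true subset difference and only the small numbers remain. Selection after randomisation is a valid concern, but its direction and size are unknown.

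Finally, Wald is not the plan's stated method. That is correct, but no interval is stated at all, and that gap is why the verdict is open.

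**Conclusion.** The finding is an unresolved contradiction over the Week 8 denominator, and one of its two readings makes the stated rule unusable. On that reading the verdict rests on about 3 versus 6 subjects (4 versus 8 if all 67 per arm are counted), selected on the primary outcome. The chance of declaring non-inferiority then runs from about 0.4% to 50%, depending on the interval method and the assumed Week 8 rate (60% to 90%, equal in both arms). The counts rest on the planning rates of 94.0% and 88.5%. Lower Week 4 relief would enlarge the group, but it would still be selected on outcome. The contradiction should be corrected, but it does not threaten the main result: the hypothesis in section 9.3 and the sample size concern Week 4 only.

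**What to change.** In section 9.2.3.2 item 1, section 8.4.1.2 and both synopsis entries (Efficacy Endpoints and Statistical Analysis Method):

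- Apply the Week 8 -0.1 rule to cumulative relief in all subjects of the analysis set. Count Week 4 responders as relieved by Week 8. For the rest use Visit 5, or the final observation including the Withdrawal visit.
- Name a score-based interval for the difference, for example Miettinen-Nurminen.
- Report relief among Treatment 2 subjects descriptively by arm, with no margin and no non-inferiority statement.
- Reconcile the definitions of non-healed (GERD-Q above 8; synopsis, Treatment period) and relief (below 8; sections 5.1 and 8.1). A score of exactly 8 falls under neither, so membership of the Treatment 2 group is itself unclear.

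No new data are needed, because GERD-Q is already scheduled at Visits 4 and 5 and at the Withdrawal visit. The cost is a protocol amendment, which under section 11.10 needs written consent of the parties and IRB approval. There is also a limit on interpretation: responders leave at Week 4, so the measure is relief achieved by Week 8, not relief sustained at Week 8, and should be labelled so.
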